7.1.2 Secondary

7.1.2.1 *Ranked secondary efficacy endpoints*

Ranked secondary efficacy endpoints (in the order of the endpoints to be tested) are:

- Change from baseline to Month 6 in DYS (VRS)
- Change from baseline to Month 6 in NMPP (VRS)
- Change from baseline to Month 6 in dyschezia (Numeric Rating Scale - NRS)
- Change from baseline to Month 6 in overall pelvic pain (NRS)
- Change from baseline to Month 6 in the interference of pain with the ability to perform daily activities, measured using the pain dimension of the Endometriosis Health Profile-30 (EHP-30)
- Change from baseline to Month 6 in dyspareunia (VRS)
- No analgesics use for EAP during the preceding 4-week period at Month 6

- No opiate use for EAP during the preceding 4-week period at Month 6

7.1.2.2 *Additional secondary efficacy endpoints*

Additional secondary efficacy endpoints include:

- Clinically meaningful reduction at scheduled visits other than Month 3 for DYS and NMPP
- Change from baseline to each scheduled assessment in the mean pelvic pain scores for DYS, NMPP and overall pelvic pain, during the previous 4-week period assessed on the NRS and VRS
- Change from baseline to each scheduled assessment in the number of days with moderate to severe pelvic pain during the previous 4-week period assessed on the VRS
- Change from baseline to each scheduled assessment in the mean worst pelvic pain score defined as the mean of the 5 highest daily pain scores reported during the previous 4-week period assessed on the NRS
- Change from baseline to each scheduled assessment in the mean of daily dyspareunia scores reported during the previous 4-week period on the dyspareunia VRS
- Change from baseline to each scheduled assessment in the mean of daily dyschezia scores reported during the previous 4-week period assessed on the dyschezia NRS
- Change from baseline to each scheduled assessment in non-opioid, opioid and combined analgesic use for EAP during the previous 4-week period based on pill count in the eDiary
- Change from baseline to each scheduled assessment in opioid analgesic use for EAP as reported in the eDiary during the previous 4-week period based on morphine milligram equivalent (MME)
- Change from baseline to each scheduled assessment in the number of days of analgesic use (including any class) for EAP during the previous 4-week period as assessed in the eDiary

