9.2 ENTRY CRITERIA

9.2.1 Inclusion Criteria

1. The subject must provide written informed consent prior to any study related procedures.
2. The subject must be a female subject aged 18 years to 49 years inclusive.
3. The subject must have had her most recent surgical and – if available – histological diagnosis of pelvic endometriosis (laparoscopy, laparotomy, vaginal fornix or other biopsy) up to 10 years before screening.
4. The subject must agree to the washout intervals for prohibited therapies (if applicable).
5. The subject must agree to switch from her usual analgesic rescue medication to only those permitted by the protocol during the Screening, Treatment and Follow-up Period.
6. The subject has moderate to severe EAP during the screening period defined as:
 - a. At the screening visit, a score of at least 2 for DYS and at least 2 for NMPP for the previous month assessed with the modified Biberoglu & Behrman (mB&B) scale.

- b. Over two full menstrual cycles (i.e. from day 1 of the first menstruation going over two spontaneous menstrual cycles up to the day before the next menstruation i.e. the third menstruation) finishing just before the baseline visit:
 - i. Mean overall pelvic pain scores of at least 4 on the 0–10 NRS over the 5 days with the highest score for each cycle separately, i.e. required for both cycles;
 - ii. At least two days with “moderate” or “severe” pain on the 0–3 VRS for pelvic pain over the days with uterine bleeding for each cycle separately, i.e. required for both cycles;
 - iii. At least two days with “moderate” or “severe” pain on the 0–3 VRS for pelvic pain over the days without uterine bleeding for each cycle separately, i.e. required for both cycles.
7. The subject is compliant with eDiary completion i.e. has completed at least 75% of days during the screening period.
8. The subject has regular menstrual cycles and the total length of the two screening menstrual cycles should be between 42 and 76 days inclusive.
9. The subject has a Body Mass Index (BMI) $\geq 18 \text{ kg/m}^2$ at the screening visit.
10. If of childbearing potential, the subject agrees to use one of the following birth control methods during the Screening Period, the entire Treatment Period of the study and until 3 months after the end of treatment:
 - a. Sexual abstinence, if this is the subject's habitual practice and/or the subject is routinely abstinent from heterosexual intercourse,
 - b. Partner with a vasectomy with confirmed azoospermia,

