2.5.1.3. Additional secondary efficacy endpoints

Additional secondary efficacy endpoints include:

- Clinically meaningful reduction at scheduled visits other than Month 3 for DYS and NMPP
- Change from baseline to each scheduled assessment in the mean pelvic pain scores for DYS, NMPP and overall pelvic pain, during the previous 4-week period assessed on the NRS and VRS

Sponsor:	ObsEva				
Protocol:	18-OBE2109-003				
Document Version No.:	V5.0	Document Date:	13-JUN-2022		

- Change from baseline to each scheduled assessment in the number of days with moderate to severe pelvic pain during the previous 4-week period assessed on the VRS
- Change from baseline to each scheduled assessment in the mean worst pelvic pain score defined as the mean of the 5 highest daily pain scores reported during the previous 4-week period assessed on the NRS
- Change from baseline to each scheduled assessment in the mean of daily dyspareunia scores reported during the previous 4-week period on the dyspareunia VRS
- Change from baseline to each scheduled assessment in the mean of daily dyschezia scores reported during the previous 4-week period assessed on the dyschezia NRS
- Change from baseline to each scheduled assessment in non-opioid, opioid and combined analgesic use for EAP during the previous 4-week period based on pill count in the eDiary
- Change from baseline to each scheduled assessment in opioid analgesic use for EAP as reported in the eDiary during the previous 4-week period based on morphine milligram equivalent (MME)
- Change from baseline to each scheduled assessment in the number of days of analgesic use (including any class) for EAP during the previous 4-week period as assessed in the eDiary
- Change from baseline to each scheduled assessment in the number of days of opioid analgesic use for EAP during the previous 4-week period as assessed in the eDiary
- Change from baseline to each scheduled assessment in the number of pelvic pain-free days (assessed on the VRS) during the previous 4-week period
- Change from baseline to each scheduled assessment in ability to perform daily activities during the previous 4-week period, as assessed in the eDiary (daily function NRS)
- Change from baseline to each scheduled assessment in the number of days with no difficulty in doing daily activities due to EAP during the previous 4-week period as assessed in the eDiary (daily function NRS)

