4.6.3.3. Change from baseline to Month 6 in overall pelvic pain (NRS)

The change from baseline to Month 6 (the last 28 days of randomized treatment up to the Month 6 visit, defined as the last 28 days prior to and including last treatment administration date as defined in Section 4.2.11 or the 28 calendar days immediately prior to and including the last dose date for subjects who discontinue treatment prior to Month 6) in overall pelvic pain using the NRS will be analyzed the same way as for dyschezia as described in Section 4.6.3.2. The baseline will be computed as the mean of the overall pelvic pain score over the two baseline menstrual cycles.

The number and percentage of subjects with a reduction of X from baseline to Month 6 for Overall Pelvic Pain will be presented. The reduction will be defined in a similar way as for the primary endpoint, but for Overall Pelvic Pain score at the Month 6 timepoint. The value for the threshold X will be obtained from the MCT analysis based on blinded Month 6 data.

4.6.3.4. Change from baseline to Month 6 in the interference of pain with the ability to perform daily activities, measured using the pain dimension of the Endometriosis Health Profile-30 (EHP-30)

The EHP-30 pain dimension consists of 11 items each addressing the effect of pain on various activities and each assessed on a 5-point scale (0=Never through to 4=Always). The EHP-30 Pain Impact Domain comprises the following items:

Sponsor:	ObsEva		
Protocol:	18-OBE2109-003		
Document Version No.:	V5.0	Document Date:	13-JUN-2022

During the last 4 weeks, because of your endometriosis, how often have you...

- 1. Been unable to go to social events because of the pain?
- 2. Been unable to do jobs around the house because of the pain?
- 3. Found it difficult to stand because of the pain?
- 4. Found it difficult to sit because of the pain?
- 5. Found it difficult to walk because of the pain?
- 6. Found it difficult to exercise or do the leisure activities you would like to do because of the pain?
- 7. Lost your appetite and/or been unable to eat because of the pain?
- 8. Been unable to sleep properly because of the pain?
- 9. Had to go to bed/lie down because of the pain?
- 10. Been unable to do the things you want because of the pain?
- 11. Felt unable to cope with the pain?

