Corresponding baseline values will be calculated based on the two baseline menstrual cycles, which may not be exactly 28 days each.

The values for other endpoints (monthly and 3-monthly questionnaires from Section 4.6.4.19 to Section 4.6.4.26) are defined as the value at the corresponding visit or value falling into the corresponding visit window as described in section 4.2.9. For these other endpoints, descriptive summaries by visit will be

Sponsor:	ObsEva		
Protocol:	18-OBE2109-00	3	
Document Version No.:	V5.0	Document Date:	13-JUN-2022

performed in two ways, once including values at the corresponding visit or value falling into the corresponding visit window as described in section 4.2.9, and once applying the while on treatment strategy, i.e., including values from the discontinued visits at each next scheduled visit.

For endpoints based on daily diary data, analyses will use observed data only in such cases, provided that a minimum number of 43% (at least 12 days of each 28-day period) completed daily eDiary entries are available.

4.6.4.1. Clinically meaningful reduction at scheduled visits other than Month 3 for DYS and NMPP

The proportion of responders for DYS and NMPP based on daily e-diary data will be reported at each visit (each 28 days period) along with odds-ratio and 97.5% confidence intervals from logistic regression as described in Section 4.6.2.1.2.

The same responder definition defined for primary endpoint in Section 4.6.2.1.1 will be used, but for other scheduled visits.

Due to the war situation in Ukraine, data from subjects in Ukraine sites may be incomplete, missing or uncleaned. The descriptive analysis of proportion of responders for DYS and NMPP at each visit will be repeated, excluding data collected after 24FEB2022 for subjects from Ukraine sites, for the Follow-up period only (Follow-up set), as the main treatment period was completed before the start of the war. Listings will contain country information to identify those subjects.

4.6.4.2. Change from baseline to each scheduled assessment in mean pelvic pain scores for DYS, NMPP and overall pelvic pain, during the previous 4-week period assessed on the NRS and VRS

The change from baseline to each scheduled assessment in mean pelvic pain scores for DYS, NMPP and overall pelvic pain will be analyzed as described for the ranked secondary endpoint in Section 4.6.3.1 (continuous summary and analysis of covariance at each visit).

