4.6.4.3. Change from baseline to each scheduled assessment in the number of days with moderate to severe pelvic pain during the previous 4-week period assessed on the VRS

The actual value and change from baseline of number of days with moderate or severe pelvic pain collected in the e-diary on the VRS will be summarized for each 28-day period. The baseline value will be computed by averaging the number of days with moderate or severe pelvic pain of the two baseline menstrual cycles. The number of days will be analyzed with a negative binomial model including baseline

Sponsor:	ObsEva		
Protocol:	18-OBE2109-003		
Document Version No.:	V5.0	Document Date:	13-JUN-2022

as a covariate. The estimated least square means treatment differences along with 97.5% CI will be provided.

SAS Code for negative binomial model with repeated measurements

```
proc genmod data=dataset order=internal ;
    class treatment;
    model nbdays = baseline treatment / dist=negbin type3 ;
    lsmeans treatment / diff = control('1') exp at means cl alpha=0.05
adjust=bon;
estimate 'TRT Placebo' intercept 1 base %sysevalf(&meanbase.) trt01pn 1 0 0 /
exp E;
estimate 'TRT LGX 75' intercept 1 base %sysevalf(&meanbase.) trt01pn 0 1 0 /
exp E;
estimate 'TRT LGX 200' intercept 1 base %sysevalf(&meanbase.) trt01pn 0 1 0 /
exp E;
estimate 'TRT LGX 200' intercept 1 base %sysevalf(&meanbase.) trt01pn 0 1 0 /
exp E;
estimate 'TRT LGX 200' intercept 1 base %sysevalf(&meanbase.) trt01pn 0 0 1
/ exp E;
    ods output lsmeans=lsm diffs=lsmd Estimates=estimate ;
```

run;

"meanbase" macro variable is the mean value of baseline over the same selection of subjects used in the model

4.6.4.4. Change from baseline to each scheduled assessment in the mean worst pelvic pain score defined as the mean of the 5 highest daily pain scores reported during the previous 4-week period assessed on the NRS

The actual value and change from baseline of the mean worst pelvic pain score, defined as the mean of the 5 highest daily pain scores reported during each 28-day period will be summarized for each 28-day period. The baseline mean worst pelvic pain score will be the average of the mean pelvic pain score of each of the two baseline menstrual cycles. An analysis of covariance will be performed for each period.

If less than 5 days of pain score data is available, the mean worst pelvic pain will be defined as the mean of the available daily pain scores.

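### SAP 4.6.4.4 sets the baseline of the mean worst pelvic pain score to an all-days mean, so reported baselines and within-group changes would be wrong if the sentence is followed literally

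*SAP*

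**What the plan says.** Protocol 7.1.2.2 has this NRS endpoint among its additional secondary ones, analysed as a change from baseline. Its wording includes: "mean worst pelvic pain score defined as the mean of the 5 highest daily pain scores reported during the previous 4-week period assessed on the". SAP 2.5.1.3 repeats this as "the mean worst pelvic pain score defined as the mean of the 5 highest daily pain scores reported during the previous 4-week period".

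SAP 4.6.4.4 gives the derivation. The score is "defined as the mean of the 5 highest daily pain scores reported during each 28-day period". The baseline follows separately: "The baseline mean worst pelvic pain score will be the average of the mean pelvic pain score of each of the two baseline menstrual cycles". Actual values and changes from baseline are to be summarised for each 28-day period, with an analysis of covariance per period. That section names no covariate; the Protocol synopsis (Secondary Efficacy Analysis) gives the baseline value as covariate for continuous endpoints in general.

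No other text supplies a five-highest-days baseline for this endpoint:
- SAP 4.2.10 leaves the details of baseline calculation to the section for each endpoint.
- The introduction to SAP 4.6.4 says only: "Corresponding baseline values will be calculated based on the two baseline menstrual cycles, which may not be exactly 28 days each".
- SAP section 5 lists no intended change to this baseline.

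**The concern.** As written, the post-baseline value and its baseline are different quantities: a mean over the five worst days, and a mean over all days of a cycle. The first cannot be smaller than the second when both are taken from the same diary, and it is larger whenever daily scores vary. Subtracting one from the other therefore builds an upward shift into every change score.

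The rule can be computed as it stands, so a programmer could follow it without noticing. At stake are the tables of baseline values and of change from baseline for a secondary endpoint that the protocol lists.

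**Working it through.** The plan gives no figure for this endpoint, so there is none to reproduce. The check compares the texts, works out the artefact for fixed diaries, and then uses a simulation to see what reaches the treatment comparison.

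**1. Texts side by side**
- The neighbouring endpoint in SAP 4.6.4.3 (days with moderate or severe pain) matches baseline to outcome: "The baseline value will be computed by averaging the number of days with moderate or severe pelvic pain of the two baseline menstrual cycles".
- The separate overall pelvic pain endpoint in SAP 4.6.3.3 uses a plain mean: "The baseline will be computed as the mean of the overall pelvic pain score over the two baseline menstrual cycles". The baseline sentence in 4.6.4.4 amounts to this, which is the baseline of a different endpoint.
- Inclusion criterion 6b(i) (Protocol 9.2.1) already needs the NRS mean "over the 5 days with the highest score for each cycle separately", with a minimum of 4. The matching baseline therefore needs no new data.

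**2. Artefact for an unchanged diary**

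Take 28 days, with the five worst days all at *w* and the other 23 days all at *r*. The apparent change when nothing has changed is

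*w* − (5*w* + 23*r*)/28 = (23/28)(*w* − *r*).

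- *w* = 4 (the eligibility minimum), *r* = 0, 1, 2, 3, 4: +3.29, +2.46, +1.64, +0.82, 0.
- *w* = 8, *r* = 1, 3, 5: +5.75, +4.11, +2.46.

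**3. Effect on the ANCOVA contrast**

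Let *Y* be the post-baseline score, *B* the baseline used and *T* treatment. The model *Y* − *B* = α + τ*T* + β*B* + ε is the same as *Y* = α + τ*T* + (β + 1)*B* + ε. Subtracting *B* leaves τ unchanged, so only the choice of covariate can matter.

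**4. Simulation**

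All inputs are assumptions, because the documents give no daily NRS distribution. They are: 150 subjects per arm, 200 replicates, subject mean 5, between-subject SD 1.3, and daily scores rounded and limited to 0–10. Each active arm has a true reduction of 1 point, placebo has none, and a between-period shift with SD 1.5 is added to each subject after baseline.

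| Daily SD | Placebo mean change, as written | Placebo mean change, matched | Gap (difference) | Treatment difference, as written | Treatment difference, matched |
|---|---|---|---|---|---|
| 1 | +1.386 | −0.019 | 1.405 | −0.988 | −0.988 |
| 1.5 | +2.012 | −0.080 | 2.092 | −0.938 | −0.941 |
| 2 | +2.627 | −0.107 | 2.734 | −0.894 | −0.893 |
| 2.5 | +3.132 | −0.160 | 3.292 | −0.810 | −0.812 |

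The standard errors of the treatment difference agree within 0.003. An all-days mean measured before randomisation is a legitimate covariate and performs about as well here.

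**5. The one route into the contrast**

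SAP 4.2.8.1 assigns a change of zero to subjects who cannot be assessed for lack of on-treatment pain data. With a matched baseline, zero is neutral. With the baseline as written, zero lies below the value that means no change, by the gap. The contrast then moves by roughly the gap times the difference between arms in the proportion assigned zero. At daily SD 2:
- 7% on active against 2% on placebo: 2.734 × 0.05 = 0.14 in favour of active. The simulated difference moved from −0.877 to −1.013.
- 12% against 2%: 2.734 × 0.10 = 0.27. The simulated difference moved from −0.829 to −1.103.

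These percentages are assumed. With equal proportions the expected shift is nil.

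**The case against.** The strongest reply is that this is a slip of the pen. The subject of the sentence is the baseline mean worst score, a term defined just before it, and the rest can be read as saying only how two cycle-level scores are combined. The endpoint definition in both documents and the eligibility score point the same way. That is probably what was meant, and the point is made here as a wording error, not as a deliberate choice of analysis. But the sentence can be executed as it stands, it remains in SAP V5.0, and SAP 4.2.10 makes it the governing text.

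The second reply is that little depends on it. The endpoint is an additional secondary one. The introduction to SAP 4.6.4 places these outside the fixed sequence and does not fully control their type I error. Post-baseline actual values are correct under either reading. All of this stands and limits the weight of the point.

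A reader might also draw three stronger conclusions, which the documents do not support:
- **That the treatment comparison is biased because the covariate is wrong.** Steps 3 and 4 show that it is essentially unchanged.
- **That the artefact exceeds a meaningful-change threshold.** The 2.7-point value in SAP 4.6.1.4 is for overall pelvic pain averaged over all days. SAP 4.6.1.1.2 lists six endpoints for supportive responder analyses, and this is not one of them, so no subject would be misclassified. In addition, only the largest of the four simulated placebo changes is clearly above 2.7.
- **That every unchanged subject would appear much worse.** The shift depends on how much daily scores vary, and it is 0 or +0.82 in two of the fixed diaries above.

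**Conclusion.** The wording is wrong as it stands and should be corrected. Followed literally, it gives baseline values that are too low and within-group changes that understate improvement or show false worsening. Under the assumed daily SDs of 1 to 2.5, an arm with no treatment effect shows a mean change of about +1.4 to +3.1 NRS points. The underlying gap is 1.4 to 3.3, because the matched change in the simulation is itself slightly below zero. For the fixed diaries, the size follows from arithmetic alone.

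The linzagolix-placebo difference is essentially unaffected. The exception is conditional: zero changes would have to be assigned for this endpoint, and at unequal rates between arms. It is not clear that the rule applies here, since the introduction to SAP 4.6.4 allows a shorter window for subjects who stop within four weeks, and SAP 4.2.8.1 expects very few subjects to be affected. No co-primary or ranked secondary result uses this baseline. Whether the programmed derivation follows the literal sentence cannot be told from the documents.

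**What to change.** In SAP 4.6.4.4, define the baseline as the average, over the two baseline menstrual cycles, of the mean of the five highest daily NRS pelvic pain scores in each cycle. This is the per-cycle score that inclusion criterion 6b(i) already uses. State in the same place whether the zero-change rule of SAP 4.2.8.1 applies to this endpoint.

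Then check the derivation program and any tables already produced. If they used the all-days mean, rerun the baseline and change summaries and the per-period ANCOVA for this endpoint. The text change is one phrase and needs no new data; the remaining cost is a program check and, at worst, reissuing the tables for one endpoint.

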4.6.4.5. Change from baseline to each scheduled assessment in mean daily dyspareunia scores

Sponsor:	ObsEva		
Protocol:	18-OBE2109-003		
Document Version No.:	V5.0	Document Date:	13-JUN-2022

reported during the previous 4-week period on the dyspareunia VRS

The actual value and change from baseline in mean daily dyspareunia scores will be summarized as a continuous variable for each 28-day period. An analysis of covariance will be performed for each period.

Subjects not sexually active for reasons other than endometriosis will have missing values for the corresponding 4-week periods. Subjects not sexually active for reasons other than endometriosis at baseline will be excluded from the analysis.

4.6.4.6. Change from baseline to each scheduled assessment in mean daily dyschezia scores reported during the previous 4-week period assessed on the dyschezia NRS

The actual value and change from baseline in mean daily dyschezia scores will be summarized as a continuous variable for each 28-day period. An analysis of covariance will be performed for each period.

4.6.4.7. Change from baseline to each scheduled assessment in non-opioid, opioid and combined analgesic use for EAP during the previous 4-week period based on pill count in the eDiary

Non-opioid, opioid and combined analgesic use for EAP will be measured using the mean of daily pill count collected in the eDiary over each 28-day period. For non-opioid and combined analgesic use, descriptive summary (actual values and changes from baseline) and analysis of covariance for each period will be performed. Due to a low number of subjects using any opioids, opioids use will not be analyzed as a continuous variable, only a listing with by subject opioid use mean daily pill count will be provided.

The number and percentage of subjects reporting no analgesic use for EAP, and the proportion of subjects reporting no opiate use for EAP at baseline and during the preceding 4-week period at Month 3 (last 28 days prior to and including last treatment administration date) will be presented. The proportion of subjects with no analgesic use for EAP, and with no opiate use for EAP will be conducted using a logistic regression model, with treatment group as the main effect. For these proportions, in addition to eDiary analgesic use, data from the concomitant medication page will be used, as described in Section 4.6.3.6.

4.6.4.8. Change from baseline to each scheduled assessment in opioid analgesic use for EAP as reported in the eDiary during the previous 4-week period based on morphine milligram

Sponsor:	ObsEva		
Protocol:	18-OBE2109-003		
Document Version No.:	V5.0	Document Date:	13-JUN-2022

equivalent (MME)

Opioid analgesic use for EAP will also be assessed based on morphine milligram equivalent (MME). The mean daily amount for each 28-day period reported in eDiary as pill count will be converted in MME.

No opioids are allowed in Ukraine. Subjects from Ukraine will therefore be excluded from the analysis in MME. If some opioids are nevertheless recorded for subjects from Ukraine, they will not be considered, as the conversion in MME would be unknown. Those opioids records will however be considered for other analgesic use analyses not requiring conversion in MME.

Due to a low number of subjects using any opioids, opioids use will not be analyzed, only a listing with by subject mean daily opioid use in MME will be provided.

4.6.4.9. Change from baseline to each scheduled assessment in the number of days of analgesic use (including any class) for EAP during the previous 4-week period as assessed in the eDiary

The actual value and change from baseline in the number of days with analgesic use for EAP collected in the e-diary will be summarized for each 28-day period. The number of days will be analyzed using a negative binomial model, including baseline as a covariate The estimated least square means treatment differences along with 97.5% CI will be provided. The baseline value will be computed by averaging the number of days with analgesic use of the two baseline menstrual cycles.

4.6.4.10. Change from baseline to each scheduled assessment in the number of days of opioid analgesic use for EAP during the previous 4-week period as assessed in the eDiary

The actual value and change from baseline in the number of days with opioid analgesic use for EAP collected in the e-diary will be calculated for each 28-day period. The baseline value will be computed by averaging the number of days with opioid analgesic use of the two baseline menstrual cycles.

Due to a low number of subjects using any opioids, number of days with opioid analgesic use will not be analyzed, only a by subject listing will be provided.

4.6.4.11. Change from baseline to each scheduled assessment in the number of pelvic pain-free days

CRS-BS-TP-000005 V 1.0

Sponsor:	ObsEva			
Protocol:	18-OBE2109-00	18-OBE2109-003		
Document Version No.:	V5.0	Document Date:	13-JUN-2022	

(assessed on the VRS) during the previous 4-week period

The actual value and change from baseline of number of pelvic pain-free days collected in the e-diary will be summarized for each 28-day period. The number of days will be analyzed with a negative binomial model, including baseline as a covariate. The estimated least square means treatment differences along with 97.5% CI will be provided. The baseline value will be computed by averaging the number of pelvic pain-free days of the two baseline menstrual cycles.

4.6.4.12. Change from baseline to each scheduled assessment in ability to perform daily activities during the previous 4-week period, as assessed in the eDiary (daily function NRS)

Daily activities score for each subject will be calculated by averaging over the corresponding 28 calendar days immediately prior to and including the day each visit (or the 28 calendar days immediately prior to and including the last dose date for subjects who discontinue treatment prior to Month 6). The baseline mean of daily activities score will be calculated by averaging over the two baseline menstrual cycles. The actual value and change from baseline of daily activities score will be each activities score will be each activities score will be calculated. The score will be summarized as a continuous variable and change from baseline for each 28-day period will be evaluated using analysis of covariance.

4.6.4.13. Change from baseline to each scheduled assessment in the number of days with no difficulty in doing daily activities due to EAP during the previous 4-week period as assessed in the eDiary (daily function NRS)

The actual value and change from baseline of number of days with no difficulty in doing daily activities due to EAP collected in the e-diary will be summarized for each 28-day period. The number of days will be analyzed with a negative binomial model, including baseline as a covariate. The estimated least square means treatment differences along with 97.5% CI will be provided. The baseline value will be computed by averaging the number of days of the two baseline menstrual cycles.

4.6.4.14. Change from baseline to each scheduled assessment in the number of days when dyspareunia was a problem during the previous 4-week period (including days when sexual intercourse was avoided because of anticipation of pain) as assessed on the dyspareunia VRS

The actual value and change from baseline of number of days with answer to Sexual Intercourse in the last 24H questionnaire is "Intercourse was interrupted due to pain" or "No, I avoided sexual intercourse because of anticipation of pain" collected in the e-diary will be summarized for each 28-day period. The number of days will be analyzed with a negative binomial model, including baseline as a covariate. The

Sponsor:	ObsEva			
Protocol:	18-OBE2109-00	18-OBE2109-003		
Document Version No.:	V5.0	Document Date:	13-JUN-2022	

estimated least square means treatment differences along with 97.5% CI will be provided. The baseline value will be computed by averaging the number of days of the two baseline menstrual cycles.

4.6.4.15. Change from baseline to each scheduled assessment in the number of days when sexual intercourse was avoided because of anticipation of pain during the previous 4-week period as assessed on the dyspareunia VRS

The actual value and change from baseline in the number of days with answer to Sexual Intercourse in the last 24H questionnaire is "No, I avoided sexual intercourse because of anticipation of pain" collected in the e-diary will be summarized for each 28-day period. The number of days will be analyzed with a negative binomial model, including baseline as a covariate. The estimated least square means treatment differences along with 97.5% CI will be provided. The baseline value will be computed by averaging the number of days of the two baseline menstrual cycles.

In addition, the proportion of days when sexual intercourse was avoided because of anticipation of pain will be also summarized for actual values and changes from baseline.

The proportion is defined as:

Number of days when sexual intercourse was avoided because of anticipation of pain/ (Number of days in period – Number of days with missing data – Number of days with no sexual intercourse for other reasons)

The number of days in each period will be equal to 28, except at baseline, for which it will be the number of days in each baseline menstrual cycle.

4.6.4.16. Change from baseline to each scheduled assessment in the number of days with uterine bleeding (including spotting) during the previous 4-week period measured by eDiary

The actual value and change from baseline in the number of days with uterine bleeding ("Bleeding", "Spotting", "Heavy Bleeding") collected in the e-diary will be summarized for each 28-day period. The number of days will be analyzed with a negative binomial model, including baseline as a covariate. The estimated least square means treatment differences along with 97.5% CI will be provided. The baseline value will be computed by averaging the number of days with uterine bleeding during the two baseline menstrual cycles.

Sponsor:	ObsEva		
Protocol:	18-OBE2109-003		
Document Version No.:	V5.0	Document Date:	13-JUN-2022

4.6.4.17. Change from baseline to each scheduled assessment in the number of days when school or work was missed due to EAP in the previous 4-week period as reported in the eDiary

The actual value and change from baseline in the number of days when school or work was missed due to EAP as collected in the e-diary will be summarized for each 28-day period. The number of days will be analyzed with a negative binomial model, including baseline as a covariate. The estimated least square means treatment differences along with 97.5% CI will be provided. The baseline value will be computed by averaging the number of days during the two baseline menstrual cycles when school or work was missed due to EAP.

4.6.4.18. Change from baseline to each scheduled assessment in the number of days when the subject had to go to bed or lie down due to EAP in the previous 4-week period as reported in the eDiary

The actual value and change from baseline in the number of days when the subject had to go to bed or lie down due to EAP as collected in the e-diary will be summarized for each 28-day period. The number of days will be analyzed using a negative binomial model, including baseline value as a covariate. The estimated least square means treatment differences along with 97.5% CI will be provided. The baseline value will be computed by averaging the number of days during the two baseline menstrual cycles when the subject had to go to bed or lie down due to EAP.

4.6.4.19. Change from baseline to each scheduled assessment in the Pain, Control and powerlessness, Emotional well-being, Social support, Self-image dimensions and the Modular sexual relationship questionnaire of EHP-30 scores

The EHP-30 is a disease-specific self-administered questionnaire used to measure health-related quality of life in women with endometriosis. The EHP-30 is composed of two parts: a core questionnaire containing five scales that are applicable to all women with endometriosis and a modular part containing six scales which do not necessarily apply to all women with endometriosis. This study will employ the Core EHP-30 and modular section C (Part 2) as outlined in Appendix D of protocol.

The questionnaire is composed of five scales and of the sexual relationship scale in the modular part:

- Pain (Questions 1-11): See Section 4.6.3.4 for items included in Pain dimension
- Control and powerlessness (Questions 12-17):
 - Generally felt unwell?
 - Felt frustrated because your symptoms are not getting better?
 - Felt frustrated because you are not able to control your symptoms?

CRS-BS-TP-000005 V 1.0

Page 79 of 127

Cytel Confidential: This is a controlled document and shall not be changed, saved, copied or reproduced by any unauthorized

Sponsor:	ObsEva		
Protocol:	18-OBE2109-00	3	
Document Version No.:	V5.0	Document Date:	13-JUN-2022

- Felt unable to forget your symptoms?
- Felt as though your symptoms are ruling your life?
- Felt your symptoms are taking away your life?
- Social support (Questions 24-27):
 - Felt unable to tell others how you feel?
 - Felt others do not understand what you are going through?
 - Felt as though others think you are whining?
 - Felt alone?
 - Emotional well-being (Questions 18-23):
 - Felt depressed?
 - Felt weepy/tearful?
 - Felt miserable?
 - Had mood swings?
 - Felt bad-tempered or short-tempered?
 - Felt violent or aggressive?
- Self-image (Questions 28-30):
 - Felt frustrated that you cannot always wear the clothes you would choose?
 - Felt your appearance has been affected?
 - Lacked confidence?
- Modular sexual relationship questionnaire

Refer to Appendix B in Section 7.2 for scoring. Each scale is standardised on a scale of 0 - 100, where 0 indicates the best health status and 100 the worst health status. Scale scores for each scale are calculated from the total of the raw scores of each item in the scale divided by the maximum possible raw score of all the items in the scale, multiplied by 100.

Each item of each scale will be summarized by category at each visit (Day 1, Month 1, Month 3, Month 6). The actual value and change from baseline of each scale score will be summarized as a continuous variable.

Each scale score will be analyzed at each visit using an analysis of covariance.

